5.4.4 Adverse events

Severity of adverse events is rated according to Common Terminology Criteria of Adverse Event (CTCAE version 4.0; R10-4848)

In the CTP, protocol-specified significant adverse events were defined as AEs which were of particular concern for safety monitoring within the trial. These AEs needed to be handled by the investigator according to the rules defined for SAE reporting (see CTP Section 5.2.2.2). The following protocol-specified significant adverse events were defined:

- Infusion-related reactions (IRR) (CTCAE grade 3 or higher)
- Tumour lysis syndrome (TLS)
- any event that qualifies for DLT
- Drug-induced liver injury (DILI)

For the definition of hepatic injury inducing alterations of liver parameters refer to the CTP Section 5.2.2.1.

Definitions of AEs by user-defined categories in terms of MedDRA codes and sub-searches can be found in Section 9.4 of this TSAP.

Other significant AEs are all serious or non-serious AEs leading to treatment discontinuation or dose reduction.

5.4.5 Laboratory parameters

5.4.5.1 General safety laboratory parameters

Original values will be converted into standard units and the CTCAE grades will be assigned to parameters which have a CTCAE definition (CTCAE version 4.0) (R10-4848)

Primary List: Tables and figures for these laboratory values and urine measurement will be displayed in Section 15 of the CTRs, if applicable.

Table 5.4.5.1: 1 List of primary laboratory parameters

Worsening direction	Laboratory	Parameter
low value	Haematology	haemoglobin (HGB)
		white blood cell count (WBC, total leukocyte count)
		platelets (thrombocytes, PLTCT)
	Differentials	neutrophils (NEUT)
	Biochemistry	inorganic phosphate (P)
high value	Enzymes	aspartate amino transferase (AST)
		alanine amino transferase (ALT)
	Substrates	creatinine (CRE)
		total bilirubin (TBILI)
	Biochemistry	lactate dehydrogenase (LDH)
		uric acid (URIC)
high and low value	Electrolytes	potassium (K)
		calcium (CA)
	Differentials	lymphocytes (lymphopenia) (LYMPH)

Secondary List: Tables for these laboratory values and urine measurement will be displayed in Appendix 16.1.9.2 of CTRs, if applicable. All laboratory values other than those in the primary list will be considered as secondary, including but not limited to the parameters listed in the following table. Urine measurement (based on dipsticks with 0, +, ++, and +++; the

more + the worse) will be displayed if needed. For urine measurement based on dipsticks conversion rules can be found in Section 9.3.

Table 5.4.5.1: 2 List of secondary laboratory parameters

Worsening direction	Laboratory	Parameter
low value	Haematology	red blood cell count (RBC)
	Differentials	CD3+ T cell count (CD3V)
		CD4+ T cell count (CD4V)
		CD8+ T cell count (CD8V)
		CD56+ natural killer cell count (CD56V)
	Biochemistry	total protein (TPRO)
		albumin (ALB)
		immunoglobulin M (IGM)
		immunoglobulin G (IGG)
	Urine	urine PH (UPH)
high value	Enzymes	alkaline phosphatase (ALKP)
8	Coagulation	international normalised ratio of prothromin time (INR)
		activated partial thromboplastin time (aPTTs)
		prothrombin time (PRTsec)
	Biochemistry	urea (UREA)
		direct bilirubin (BILID)
	Urine	urine glucose (UGLU)
		urine nitrite (UNIT)
		urine protein (UPROZ)
		urine erythrocytes (URBCZ)
		urine leukocytes (UWBCZ)
high and low value	Haematology	reticulocytes (RET)
-		haematocrit (HCT)
	Differentials	CD19+ B cell count (CD19V)

Table 5.4.5.1: 2 List of secondary laboratory parameters (cont.)

Worsening direction	Laboratory	Parameter
	Differentials	monocytes (MONO)
		basophils (BAS)
		eosinophils (EOS)
	Electrolytes	sodium (NA)
	Substrates	glucose (GLUA, GLUB)
	Biochemistry	immunoglobulin A (IGA)

5.4.5.2 Laboratory values of special interest

Neutropenia, thrombocytopenia and leukopenia

Episodes of low neutrophil, platelets and WBC counts are of special interest. Episodes with CTCAE grade 3 and 4 and CTCAE grade 4 lasting 7 or more days will be analyzed.

An episode of e.g. low neutrophils starts with the first occurrence of a CTCAE grade ≥ 3 and lasts until the first time the CTCAE grade falls back to ≤ 2 .

In case the episode starts during EOT or Follow-up, the duration of this episode is defined to be missing. The reason for this approach is that after EOT laboratory data is only captured infrequently and therefore the duration of an episode would be overestimated due to lack of data.

If the episode starts before EOT and the CTCAE grade of the respective parameter does not fall back to grade ≤ 2 and the patient dies, the end of the episode is defined by the date of death. If the episode starts before EOT and lasts during Follow-up the episode is censored with the date of DBL.

Hepatic enzyme elevations (potential Hy's law cases)

Special attention will be paid to patients fulfilling the criteria for potential Hy's law cases. These are defined as those cases where a combination of all of the following events occurred: any on-treatment value of ALT and/or AST > 3 times upper limit of normal (3 x ULN) with total bilirubin \ge 2 x ULN and ALKP < 2 x ULN. The events can occur in any order, but must occur within 14 days of the previous event, i.e. the second event must occur within 14 days of the first event, and the third event must occur within 14 days of the second event.

Possible clinically significant abnormal lab values

Possible clinical significance based on CTCAE grading is defined as CTCAE grade 2 or higher with an increase of at least one CTCAE grade from baseline, please refer to Section
9.2. for further details. If the baseline value is missing, all post-baseline values with CTCAE

grade 2 or higher will be classified as possibly clinically significant. For the laboratory parameters recorded that do not have a CTCAE grading defined, the BI default rules for clinical significance should be applied (5).

Tumour lysis syndrome (TLS)

The presence of laboratory TLS will be considered according to Cairo-Bishop classification. Under this system, laboratory TLS is investigated based on the serum values of uric acid, potassium, inorganic phosphate, and calcium. TLS is considered to be present if within the time window of 3 days before until 7 days after administration of BI 836826, two or more of these laboratory parameters are abnormal, or change from baseline by ≥25%.

Table 5.4.5.2: 1 Definition of abnormal laboratory values according to Cairo Bishop

Laboratory parameter	abnormal Value	Change from baseline
Uric acid	≥476 µmol/L or 8 mg/dL	≥25% increase
Potassium	\geq 6.0 mmol/L or 6 mg/L	≥25% increase
Inorganic phosphate	≥1.45 mmol/L	≥25% increase
Calcium	≤1.75 mmol/L	≥25% decrease

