# • Grade 4 thrombocytopenia lasting more than 7 days, or grade 3-4 thrombocytopenia with clinically significant bleeding

#### • Grade 4 anemia

**Less severe** haematological adverse events are frequently pre-existing in CLL patients, are usually manageable with routine supportive measures and are therefore not considered as adverse events relevant for DLT definition. Nevertheless, haematological adverse events will be considered for definition of the dose for further development.

The MTD will be defined on the basis of DLT observed during the first treatment course. However, for those patients who receive more than one dose of BI 836826, all adverse events corresponding to the above definition of DLT will be considered for the purpose of confirming the MTD and for the selection of the recommended dose for treatment of the expansion cohort and for further development. In regular intervals, all available safety data including adverse events qualifying for DLT will be submitted to the DSMB. The DSMB will independently assess this information and provide recommendations for trial conduct and dose escalation.

All DLTs, occurring during the first or repeated treatment course will be reported as significant adverse events.

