#### 5.2.3 Assessment of safety laboratory parameters

5.2.3.1 General safety laboratory parameters

Blood samples and urine have to be collected at the time points specified in the Flow Chart. Blood samples should be collected more frequently in case of relevant toxicities; e.g. in case of grade 4 neutropenia or thrombocytopenia, to document as accurately as possible the duration of the AE. Safety laboratory examinations will include haematology, biochemistry, coagulation and qualitative urine analysis:

Haematology	Haemoglobin, red blood cell count (RBC), white blood cell count (WBC) with differential, platelets (PLT)
	Reticulocytes have to be measured only at Screening, Visit 1, Day 1 of each treatment course, at the EOT visit and during follow-up.
Biochemistry	Glucose, sodium, potassium, calcium, inorganic phosphate, creatinine, aspartate amino transferase (AST), alanine amino transferase (ALT), alkaline phosphatase (AP), lactate dehydrogenase (LDH), total bilirubin (if elevated provide direct bilirubin), urea, total protein, albumin, uric acid
	Serum immunoglobulin levels (IgG, IgM, IgA), direct antiglobulin test have to be measured only at Screening, Visit 1, Day 1 of each treatment course, at the EOT visit and during follow-up.
Coagulation	Activated partial thromboplastin time (aPTT), prothrombin time (PT), international normalised ratio (INR) where indicated (e.g. treatment with vitamin K antagonists)
Urine	pH, glucose, erythrocytes, leukocytes, protein, nitrite will be analysed by dipstick and reported as semiquantitative measurements. In case of pathological findings, further evaluation should be performed and results documented.
Pregnancy test	A serum pregnancy test needs to be obtained at the time points indicated in the Flow Chart in patients of childbearing potential.

In case a treatment course is delayed due to an adverse event, the patient should visit the site at least once a week for assessment of safety laboratory and adverse events. More frequent visits may be appropriate as assessed by the investigator.

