7.8.1.2 Adverse events

Unless otherwise specified, adverse events analysis will be performed for on-treatment periods. Selected analyses (e.g. summary of AEs) will be repeated for the MTD evaluation period.

The analyses of AEs will be descriptive in nature and will follow the standard procedure laid down in the DM & SM (including all required tables and listings; guideline _'Handling and Summarization of AE Data for CTR and Integrated Summaries' (4). AEs will be coded with the most recent version of Medical Dictionary for Regulatory Activities (MedDRA). The version number will be displayed as a footnote in the respective tables and listings.

The system organ classes will be sorted alphabetically. In tables displaying AEs by dose cohort preferred terms will be sorted by descending frequency of adverse events in the "Total" BI 836826 group.

Each patient can be observed during the trial under several doses. Analysing the AE of all treatment courses will be carried out under the initial treatment. No formal statistical analysis is planned for the safety comparison.

The analysis of AEs will be based on the concept of treatment emergent AEs. That means that all adverse events occurring between first administration of BI 836826 until 6 weeks after last administration of BI 836826 will be assigned to the on-treatment period. All adverse events occurring before first administration of BI 836826 will be assigned to "Screening" and all adverse events occurring after last administration of BI 836826 + 6 weeks will be assigned to "post-study (for listings only). The actual planned dosage of BI 836826 administered on the day each AE starts will also be derived and will be included in the listing. Listings of screening events will not be sorted by initial treatment. Post-study listings will be sorted by initial treatment. For details on the treatment definition please refer to Section 6.1.

According to the BI standards, multiple recordings of AEs will be collapsed to episodes on the lowest level term and multiple episodes will be condensed to records on the PT and system organ class (SOC) level. CTCAE grade will be an additional criterion for collapsing and condensing AEs. The maximum CTCAE grade will be assigned to episodes and records. CTCAE grade and DLT information will be displayed in AE listings. MedDRA levels for condensing will be SOC and PT.

An overall summary of adverse events will be presented.

Reporting of CTCAE grades

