For Uric Acid and Hypokalemia, the CTCAE grade cannot always be assigned by the laboratory parameter itself as two different CTCAE grades have the same laboratory constellation, but are distinguished by additional clinical parameter. In this case a CTCAE grade of -1 will be assigned initially. Patients with a CTCAE grade of -1 will be treated as

- Grade 1 for Uric Acid
- Grade 1 for Hypokalemia

for all analyses. In laboratory listings, the CTCAE grade will be displayed as -1.

Patients with hepatic enzyme elevation will be tabulated. With respect to neutropenia, thrombocytopenia and leukopenia episodes the number of episodes and mean and median duration will be displayed. Additionally, laboratory values of special interest as described in Section 5.4.5 will be analyzed.

Additionally, a frequency table displaying number of patients with episodes of grade 4 neutropenia and concomitant AEs in the user-defined AE category (UDAEC) of any grade and grade 3/4 will be provided. In this context, concomitant AE is defined as AE with onset date within the neutropenia episode. The same table will be done for grade 3/4 episodes of neutropenia and concomitant AEs in the UDAEC of any grade and grade 3/4 will be done. The same applies for the display of patients with thrombocytopenia and bleeding events. For the definitions of neutropenia, thrombocytopenia and leukopenia episodes please refer to Section 5.2.5.2.

The prioritized laboratory values (see Section 5.4.5) will be displayed in Section 15 of the final CTR while all other laboratory parameters will be displayed in the Appendix of the CTR.

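### SAP 5.4.5.2 sets to missing the duration of every grade 3 or higher cytopenia episode first seen at EOT or follow-up, even where extra blood counts would let it be measured

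*SAP*

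**What the plan says.** SAP 5.4.5.2 defines an episode from laboratory counts. It starts at the first grade 3 or higher value and "lasts until the first time the CTCAE grade falls back to" grade 2 or lower. Two rules then apply:

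- Onset at EOT or later: "In case the episode starts during EOT or Follow-up, the duration of this episode is defined to be missing". The reason is that "after EOT laboratory data is only captured infrequently and therefore the duration of an episode would be overestimated due to lack of data".
- Onset before EOT: "If the episode starts before EOT and lasts during Follow-up the episode is censored with the date of DBL".

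The results go into SAP 7.8.2: "With respect to neutropenia, thrombocytopenia and leukopenia episodes the number of episodes and mean and median duration will be displayed". SAP 5.4.5.2 also calls for an analysis of grade 4 episodes lasting 7 or more days.

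The protocol treats duration as something to be measured. Section 5.2.3.1 says more frequent samples should be taken in relevant toxicities, for example "in case of grade 4 neutropenia or thrombocytopenia, to document as accurately as possible the duration of the AE". Section 3.2 says more frequent follow-up visits may be indicated for unresolved laboratory findings, and section 6.2.3.2 allows follow-up visits earlier than the usual 4-week interval.

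The SAP's safety period extends well past EOT. Under SAP 7.8.1.2, "all adverse events occurring between first administration of BI 836826 until 6 weeks after last administration of BI 836826 will be assigned to the on-treatment" phase, whereas EOT is 14 (±2) days after the last dose.

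**The concern.** The rule decides by visit label whether a duration exists and does not look at the counts. A patient whose neutrophils first reach grade 4 at EOT, and who is then sampled every 2 or 3 days until recovery, has a well-measured duration that the SAP discards. An episode without a duration cannot enter the mean, the median or the 7-or-more-days category.

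The SAP's concern about overestimation is also applied unevenly. An episode starting just before EOT and lasting into follow-up is kept and, read literally, carried to the date of database lock, which may be long after the last count.

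At stake is the descriptive picture of how long severe cytopenia lasts in each dose cohort. Protocol 5.2.1.1 says that "haematological adverse events will be considered for definition of the dose for further development". That sentence concerns adverse events rather than this laboratory derivation, but the duration summary is evidence a reader would put beside it.

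**Working it through.** The documents state no expected loss, so there is no plan figure to reproduce. The check is calendar arithmetic.

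**Inputs.** Courses last 14 days (protocol flow charts). Course 1 is dosed on days 1 and 2, later courses on day 1 (Protocol 4.1). The last scheduled count before EOT is day 8 of the last course (flow charts). EOT is last dose + 14 days (Protocol 6.2.3.1). On-treatment ends at last dose + 42 days (SAP 7.8.1.2, 6 × 7). Scheduled follow-up is 4-weekly (Protocol 6.2.3.2). Assumptions: no course delays, no unscheduled samples, and the two-portion course 1.

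**Step 1: affected part of the on-treatment period.** For k courses, the last course starts on day S = 14(k−1)+1. The last dose is on day L = 2 if k = 1, otherwise L = S. The last pre-EOT count is on day V = S+7, EOT on day E = L+14, and on-treatment ends on day T = L+42. Onset after V is first seen at EOT or later: T−V days. Onset after EOT itself: T−E = 28 days.

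| k | T | T−V | (T−V)/T | 28/T |
|---|---|---|---|---|
| 1 | 44 | 36 | 82% | 64% |
| 2 | 57 | 35 | 61% | 49% |
| 3 | 71 | 35 | 49% | 39% |
| 4 | 85 | 35 | 41% | 33% |
| 8 | 141 | 35 | 25% | 20% |

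These are shares of time. They become shares of episodes only if onset is uniform over the period.

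**Step 2: dependence on onset.** If every episode begins by the day-8 count of its course, the loss is about 0. SAP 5.2.2 describes an immediate change in blood parameters after infusion, so early onset is possible. Unscheduled counts between day 8 and EOT also lower the shares.

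**Step 3: dependence on the word Follow-up.** Step 1 takes it as the visits after EOT, which fits the reason given in SAP 5.4.5.2. SAP Table 6.1:1 instead starts a period of that name after the residual effect period. On that reading, the only on-treatment episodes affected are those first seen at the EOT visit, with onset between V and E: 16−8 = 8 days for k = 1 and 7 days otherwise. The shares become 8/44 = 18%, 7/85 = 8% and 7/141 = 5% for 1, 4 and 8 courses.

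**Step 4: who is affected.** The affected days are 36 or 35 for everyone; only the denominator changes. If a fraction s of patients stop early with h times the daily risk of the others, they supply s·h/(s·h + 1 − s) of the missing durations:

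- s = 0.2: 20%, 33% and 43% for h = 1, 2 and 3.
- s = 0.4: 40%, 57% and 67% for h = 1, 2 and 3.

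The documents give neither s nor h.

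**Step 5: is the SAP's reason sound?** Take an episode first seen at EOT with true remaining duration d, and counts every g days. The first-recovered-value rule records ⌈d/g⌉·g.

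- g = 28: any d up to 28 is recorded as 28, so every such episode counts as 7 or more days.
- g = 7: d of 2 to 6 is recorded as 7, and 8 as 14.
- g = 2 or 3: the error is at most 1 or 2 days.

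The reason holds for 4-weekly counts and fails where the protocol's extra counts were taken.

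**The case against.** The strongest defence is that the rule is explicit, reasoned and limited.

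- **Sparse data do mislead.** On scheduled follow-up counts alone, a kept duration would be overstated (Step 5). Two low values 28 days apart are not a safe minimum either, because recovery and relapse between them cannot be excluded. This stands, and any replacement must respect it.
- **Little is removed.** The episode is still counted. Worst grade, grade transitions, individual count curves and neutrophil nadir are reported (SAP 7.5.2, 7.8.2), as are AEs to 42 days after the last dose and DLTs over all courses (SAP 7.8.1). This stands: only the duration is lost.
- **The extra sampling is not mandatory.** Protocol 5.2.3.1 says should, and names grade 4 neutropenia and thrombocytopenia only as examples, while the SAP rule also covers grade 3 and leukopenia. The sentence came with the March 2015 amendment, so earlier patients were not covered. This limits how many durations can be recovered. It does not justify discarding those that were measured.

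A reader might infer that the rule removes prolonged cytopenia mainly in patients who stop early, because a low count at the planned re-dosing visit keeps its duration if dosing continues and loses it if the visit becomes EOT. The documents do not support that. Protocol 4.1.4 has counts that fail the re-dosing criteria re-evaluated for up to three weeks, and 5.2.3.1 asks for at least weekly safety laboratory tests while a course is delayed for an adverse event. An episode found then starts before EOT and keeps its duration. Step 4 shows that mainly would need an early-stop rate and a risk ratio that are not given.

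**Conclusion.** The point holds in a limited form. The rule is unconditional and discards duration even where the counts would allow it to be measured. It affects the mean and median duration and the 7-or-more-days grade 4 category. It reaches the last 28 days of the on-treatment period, or about 35 days counted from the last scheduled day-8 sample, if Follow-up means the visits after EOT.

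Under uniform onset and scheduled samples only, that is about 82%, 41% and 25% of the period for 1, 4 and 8 courses. These figures show exposure to the rule and are not estimates of loss, which could be near 0 with onset by day 8. The affected share is larger in patients with fewer courses, but a concentration of the loss in early stoppers is not shown.

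A reader might also infer that the MTD or the DLT count is understated. It is not: the MTD rests on course-1 DLTs (Protocol 5.2.1.1), and DLTs are adverse events tabulated separately from this laboratory derivation. This is a cheap improvement to a descriptive safety summary.

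**What to change.** Replace the blanket rule in SAP 5.4.5.2. For neutrophil, platelet and white cell episodes that start on treatment (to 42 days after the last dose) and are first seen at EOT or later:

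1. Use all scheduled and unscheduled counts. Derive a duration when successive values are no further apart than a pre-specified maximum gap, for example 7 days.
2. Treat the end as interval-censored between the last qualifying and the first recovered value. If no recovered value follows, give the observed span as a minimum.
3. Count an episode as grade 4 lasting 7 or more days only when the span from the first to the last grade 4 value reaches 7 days. At a 7-day gap, using the first recovered value would count a 2-day episode (Step 5).
4. Where the gap is exceeded or only one value exists, leave the duration undetermined. Report the number of such episodes by dose cohort and grade.
5. State whether Follow-up here means the visits after EOT or the period in SAP Table 6.1:1.

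The cost is SAP wording and a small programming change on data already collected. The downside is that some durations become intervals or minimum values and are less precise than those measured during a course. Patients without extra counts stay undetermined, which meets the SAP's own concern.

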6. GENERAL ANALYSIS DEFINITIONS

6.1 TREATMENTS

In this Phase I trial, treatments are not randomised (open-label, dose escalation). Different dose levels of BI 836826 are being administered. The data will be presented for all dose cohorts separately and in total over all dose cohorts. To justify the MTD determination, DLTs occurring during the MTD evaluation period (during the first treatment course) will be presented separately from those occurring during the complete on-treatment period.

"Analysing treatment" will be used for reporting of treatment emergent adverse events (AE) and to differentiate between screening, on-treatment, post-treatment and post-study safety data. The inequalities start date \leq onset date of AE < end date will determine whether the AE will be assigned to the "analysing treatment" or not. Table 6.1:1 defines the "analysing treatment period" which will be used for reporting of treatment emergent AEs and safety laboratory parameters. Safety data recorded during the Residual Effect Period (REP) will be considered as on-treatment.

If not specified otherwise, all safety tables will be based on the on-treatment period. AEs that have an onset date during the screening or post-study periods will be displayed in separate listings from those occurred during the on-treatment period.

T 11 (1	1 D C '.'	C 1 .		. 1()
Table 6 1:	I Definition	of analysing	treatment	neriodist
I dolo o.i.	1 Dominion	OI unui yonii 🗲	, u cuuniciit	periodisi

Analysing treatment period	Start date (including)	Stop date (excluding)	
Screening	Date of informed consent	Date of first administration of study medication	
On-treatment	Date of first administration of study medication	Start date of 'Follow-up'	
Follow-up	Date of end of REP +1	Start date of 'Post-study'	
Post-study	Last date patient status obtained / last date patient known to be alive + 1 (if patient is lost to follow-up) / date of refusal + 1 day / the date patient died + 1	During the trial: open / empty; after database lock (DBL): DBL + 1 day	

The initial study medication assigned at the beginning of the first treatment course will be used as the label of the analysing treatment.

The actual dose of study medication administered on the day each AE started will also be derived. This will be presented in patient listings, but will not be used for defining treatments for analysis.

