7. PLANNED ANALYSIS

For End-Of-Text tables, the set of summary statistics is: N / Mean / standard deviation [StD] / Min / Median / Max. Efficacy data are presented by dose cohort. Displays of safety data will be presented by dose cohort and in total.

For tables that are provided for endpoints with some extreme data, median, quartiles and percentiles should be preferred to mean, StD, min and max.

For time-to-event analysis tables, the set of statistics is: number of patients [N(%)], Number of patients with event [N(%)], <Time to event> [months] followed by P25 (25th percentile), median, P75 (75th percentile), Number of patients censored [N(%)]. If not specified otherwise, the duration as well as the time to event will be displayed in months and a final decision will be made at the last BRPM.

Tabulations of frequencies for categorical data will include all possible categories and will display the number of observations in a category as well as the percentage (%) relative to the respective treatment group (unless otherwise specified, all patients in the respective patient set whether they have non-missing values or not). Percentages will be rounded to one decimal place. The category missing will be displayed only if there are actually missing values. The denominator of the main categories is defined by the number of patients in the used patient set. The main categories define the denominators of the subcategories. Subcategories should be intended and "[N(%)]" will be displayed only for the main category. If a table includes only categorical data, "[N(%)]" is to be displayed in the column header.

If applicable, conversion from days to weeks, months and years will be as follows:

- Weeks = Days/7
- Months = $(Days \times 12)/365.25$
- Years = Days/365.25

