7.8.2 Laboratory data

The analyses of laboratory data will be descriptive in nature and will follow the standard procedure laid down in the SOP_"Display and Analysis of Laboratory Data" (5). Patients will be counted under the initial treatment. The analysis of laboratory data will use the same 'analysing treatments' as described for the AEs, except for that the baseline laboratory value (as defined in Section 6.7) will be included in the 'on treatment' period. Patients having at least one post-baseline laboratory value will be displayed in the descriptive analyses. Patients with missing CTCAE grade at baseline or no baseline value but with post-baseline laboratory values will be displayed in the category "Missing CTCAE grade at baseline"

Single time courses by initial treatment will be used to display converted laboratory values over time by dose cohort. The graphs may be truncated if sufficient data is not available. These graphs will be displayed in Chapter 16.1.9.2 for the following parameters.

Haematology: haemoglobin, WBC count and platelets

Differentials: neutrophils (absolute count), absolute lymphocyte count, and natural killer (NK) cells

Enzymes: LDH

Clinically relevant abnormalities (as defined in Section 5.4.5.1) will also be summarised.

Descriptive statistics, including change from baseline, frequency of patients with transitions relative to the references range, will be provided. No post-study laboratory values will be considered. CTCAE grade for applicable laboratory parameters will be calculated according to CTCAE v4.0. The following outputs will be presented:

- Baseline, last value and difference from baseline
- Worst CTCAE grade experienced during the on-treatment period
- Transitions of the CTCAE grade from baseline to the worst lab values, from baseline to the last lab values, and from the worst to last values during the on-treatment period
- Possible clinically significant laboratory values

Note: For calculating the change in CTCAE grade from baseline, patients with a CTCAE grade of -9 (no CTCAE grade defined) will be treated as a CTCAE grade 0 for all analyses. In laboratory listings, the CTCAE grade is displayed as -9.

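### Cytopenia episodes still unresolved in follow-up are censored at database lock, generally after the last blood count, and the SAP does not say how censored episodes enter the mean and median duration

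*SAP*

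**What the plan says.** SAP 5.4.5.2 starts an episode at the first value of CTCAE grade 3 or higher. The episode "lasts until the first time the CTCAE grade falls back to" grade 2 or lower. Three special cases follow.

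- An episode that starts at EOT or in follow-up gets a missing duration. The reason given is that laboratory data are sparse after EOT, "therefore the duration of an episode would be overestimated due to lack of data".
- An episode that starts before EOT in a patient who dies without recovery ends at the date of death.
- For the remaining case: "If the episode starts before EOT and lasts during Follow-up the episode is censored with the date of DBL".

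SAP 7.8.2 gives the output: "With respect to neutropenia, thrombocytopenia and leukopenia episodes the number of episodes and mean and median duration will be displayed". It says nothing about censored episodes.

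The protocol sets the length of laboratory observation. Under CTP 6.2.3.2, follow-up visits with haematology take place every four weeks for six months after EOT. They stop earlier on loss to follow-up, on new anti-neoplastic therapy, or by agreement of investigator and sponsor. Under CTP 5.2.2.2, an adverse event still present at EOT is followed until recovery or until it is sufficiently characterised. CTP 6.2.3.3 places the analysis after the final visit of the last patient.

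**The concern.** A censoring date should be the last date on which the patient was known to be still in the state. Lock is an administrative date, the same for everyone, and for most patients it comes after the last blood count. Censoring there asserts that the count stayed at grade 3 or worse through a period in which nobody measured it.

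The section avoids this error one paragraph earlier, when it declines to compute durations from sparse post-EOT data. The SAP also avoids it elsewhere: Tables 5.2.2:1 and 5.2.2:2 censor event-free PFS and FFS at the last response assessment.

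What is at stake is the reported duration of cytopenias, which the SAP lists among laboratory values of special interest. If the censored times are treated as durations, one unresolved episode can dominate a mean, and safety tables are shown by dose cohort, where cells are small.

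**Working it through.** The plan states no duration figure, so there is none to reproduce. The check has four steps.

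**1. How long can scheduled samples show an episode?** Inputs: 14-day courses and EOT 14 days after the last dose (CTP flow charts); six months taken as 183 days; onset on day 8 of course 1; no delays and no extra visits. For c courses (c of 2 or more), EOT falls on day 14(c − 1) + 1 + 14, and the last scheduled follow-up is 183 days later.

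- c = 4: EOT day 57, last visit day 240, longest observable duration 240 − 8 = 232 days.
- c = 8: EOT day 113, last visit day 296, longest observable duration 296 − 8 = 288 days.

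Under this schedule, any longer reported duration contains time without a scheduled sample.

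**2. Effect on a mean.** If censored times are averaged as durations, the mean rises by p × G. Here p is the share of episodes carried to lock and G is the gap from last value to lock. The documents give neither. Assumptions: lock on 13 Oct 2016 (the date of the revised SAP, used only as a stand-in); EOT on 1 Sep 2015 or 1 Jun 2013, so 408 or 1230 days before lock; last value 183 or 28 days after EOT; p from 5% to 20%.

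| EOT to lock (days) | Last value after EOT (days) | G (days) | Added to mean, p = 5% to 20% (days) |
|---|---|---|---|
| 408 | 183 | 225 | 11 to 45 |
| 1230 | 183 | 1047 | 52 to 209 |
| 408 | 28 | 380 | 19 to 76 |
| 1230 | 28 | 1202 | 60 to 240 |

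If sampling continues to lock, G = 0 and nothing is added.

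**3. Effect on a median.** Take an episode starting just before EOT and unresolved at the last value, 183 days later.

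- With one other episode of 10 days, mean and median coincide. They go from (183 + 10)/2 = 96.5 days to (408 + 10)/2 = 209 or (1230 + 10)/2 = 620 days.
- With two others of 10 days, the mean goes from 203/3 = 67.7 to 428/3 = 142.7 or 1250/3 = 416.7 days, and the median stays at 10.
- With nine resolved at 5, 6, 7, 8, 9, 10, 12, 14 and 21 days (sum 92) and one unresolved at day 28, the mean is (92 + 28)/10 = 12.0 days. With a 365-day gap it is (92 + 393)/10 = 48.5. The median is 9.5 both times.

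**4. Does Kaplan-Meier alone cure it?** Usually nearly, but not always. Suppose six episodes resolve at 10, 20, 40, 60, 90 and 120 days and four are unresolved with a last value at day 28.

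- Censored at day 28, survival is 0.9, 0.8, then 0.8 × 3/4 = 0.6 at day 40 and 0.6 × 2/3 = 0.4 at day 60. The median is 60 days.
- Censored 365 days later, at day 393, all four stay in the risk set. Survival reaches 0.5 at day 90, so the median is 90 days.

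The censoring date therefore has to change as well as the summary statistic.

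**The case against.** **The SAP says the episode is censored, not ended.** For death it defines an end; for lock it marks the duration as incomplete. SAP 7 also has a general provision, "For time-to-event analysis tables, the set of statistics is", followed by quartiles and the number censored, and for extreme data it says "median, quartiles and percentiles should be preferred to mean, StD, min and max". These could be taken to govern the episode table. This stands in part: it makes the inflated mean conditional. But 7.8.2 still names a mean and does not classify the table as time-to-event, and Kaplan-Meier is named only for PFS and FFS. It also leaves the censoring date at lock.

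**Observation may continue.** A clinically relevant cytopenia is an adverse event, and CTP 5.2.2.2 requires follow-up of events persisting at EOT. This stands as an exception. It does not cover events that are closed as sufficiently characterised or patients lost to follow-up.

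**The two rules cover different onsets.** Episodes starting before EOT begin under denser sampling, so the missing-duration rule need not apply to them. That is fair for the onset date. The end date, however, lies in the same sparse period.

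**Other sources are unseen.** The sponsor's laboratory guideline cited in 7.8.2 and the technical data plan may contain a rule. The SAP does not refer to either for this point.

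A reader might also infer more than the text supports:

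- That the rule uses excluded data, since 7.8.2 says "No post-study laboratory values will be considered". A censoring date is not a laboratory value, so no excluded value is used.
- That an episode resolving at a follow-up visit is also carried to lock. The general end rule comes first, and the sentence follows one about grades that do not fall back, so it is naturally read as covering unresolved episodes only.
- That the dose comparison is biased. Dose groups fill in order of admission (CTP 7.5), so gaps may tend to be longer at lower doses. This is possible but not shown.

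**Conclusion.** The point holds, and it is minor. The stated rule generally adds unobserved time as grade 3 or worse, contrary to the section's own reasoning and to the censoring convention used for PFS and FFS. The handling of censored episodes in the mean and median is not stated in the SAP.

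Whether the reported figures are inflated depends on those times being averaged as durations. If they are, the mean is affected, and the median mainly in very small cells. The amount cannot be determined: the lock date, the EOT dates, the share unresolved and the episode lengths used above are all assumptions, and the gap is zero for an event measured up to lock.

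Only a living patient whose episode starts before EOT and is unresolved in follow-up is affected. The table is descriptive, and DLT counts and the MTD do not draw on it.

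**What to change.** In SAP 5.4.5.2, replace lock as the censoring date. An episode unresolved at the last available measurement of that parameter is censored at the date of that measurement. The rule for death and the end at the first value of grade 2 or lower stay as they are.

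In SAP 7.8.2, report the number of unresolved episodes with a Kaplan-Meier median, or summarise resolved and unresolved episodes separately. Either replaces a mean that includes time up to lock.

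The cost is one sentence in each section and a change of summary statistic. No new data are needed.
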